# 12.2 Sample Size Considerations

The R34 pilot study provided estimates of effect size used for sample size calculations, which ranged greatly across measures for children with ASD. Figure 1 shows the N required to detect a difference between dental environments based on the results from the pilot study. As these effect sizes were typically smaller than those found by Shapiro et al., $^{50-51}$  they represent a more conservative estimate of sample size, and have the benefit of being specific to the population and measures proposed here. Sample size estimates were computed to detect the effect of the repeated measurement environment for outcomes specified in the primary objective, with EDA being the primary outcome (Hyp 1) and distress behavior, perception of pain, and sensory discomfort secondary, with 1-=0.80 and -=0.025 (Hyp 2). In the R34 pilot study, the effect sizes for EDA difference between environments ranged from Cohen's d = 0.44-0.46 (see Figure

1). The effect size of the environment difference for sensory discomfort and pain intensity were large (d's = 0.69 and 0.62, respectively), while distress behavior measure effects were small (d's ranging from 0.11 to 0.23), likely due to the restricted range of answers in those measures. Attrition in the pilot data was extremely low (2%), however the more conservative attrition estimate of 10% was used for these calculations. Thus we will recruit 220 children with ASD, anticipating having repeated measures on 165. This N will allow for the detection of a within group change attributable to environment of Cohen's d = 0.22. Figure 1 shows the estimated sample size, including the effect sizes from the R34; as indicated, our target sample size, after attrition, should have sufficient power to detect differences in our primary outcome.

[figure not shown]

Figure 1. Sample size estimates based on ASD participants of R34 Pilot and Feasibility Study

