# 12.4 Final Analysis Plan

Descriptive statistics will be performed for all variables of interest to describe the participant population at baseline, including attrition rate and missing data, to compare those randomized to SADE first vs. those randomized to RDE first. We anticipate a low attrition rate (~10%) and will impute missing data for intent-to-treat analyses using Markov Chain Monte Carlo (MCMC)

imputation with multiple values imputer for each missing value averaged for an estimation for analyses. Bivariate associations between outcomes (physiological anxiety and children's negative behavioral responses), environment (SADE or RDE), and covariates (age, gender, order of visit, autism severity, IQ, and sensory sensitivity) will be described. The primary objective of determining difference between dental environments will be tested using intent-to-treat models examining the within-subject factor of dental environment (SADE vs RDE) using repeated measures ANCOVA for each outcome. *A priori* covariates include age (continuous), randomized order of visit, gender, and temperature. Other participant characteristics that are unbalanced between order of visits will be included as covariates *ad hoc*.

The secondary objective of examining the mediating effect of physiologic response on behavioral outcomes will be tested by first examining the bivariate relationships between EDA and behavioral outcomes, and then adding EDA estimates (SCL and NS-SCR) to models of dental environment difference on behavioral outcomes, and examining the change in the within group coefficients. A change in coefficient >15% will be considered evidence of mediation. While we have several outcomes, we specify only one mediator, thus we will apply a rational approach to examination of multiple outcomes, and will assess the fidelity of our study by estimating effect sizes (Cohen's d) of the dental environment before and after the mediation factors are assessed to confirm that statistical results were supported by clinical relevance of findings. If physiological anxiety does mediate the environment's effect on negative behavioral responses, we anticipate that the anticipated effect of environment will be eliminated once we add in EDA to the models specified in Hypothesis 2. Analyses will be performed using SPSS (v.22); a priori two-sided  $\square = 0.05$ .

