# **Secondary Objective 3: Hypothesis 3**

Hypothesis 3 seeks to test the degree to which physiological anxiety mediates the effect of the SADE intervention's impact on negative behavior. To test this hypothesis, we will add to the model for Hypothesis 2 above and look at the change in the coefficient and effect size of  $B_1$  as well as the effect of EDA ( $B_2$ ) on negative behavior.

Hyp 3: Negative behavior =  $B_0 + B_1$ \*Environment +  $B_2$ \*EDA + Covariates

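### The rule that a change in coefficient above 15% shows mediation has no test behind it; for the distress outcomes chance alone meets it in about 17–31% of trials

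*Combined protocol and SAP*

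**What the plan says.** Section 12.4 (Final Analysis Plan) describes the mediation analysis as "adding EDA estimates (SCL and NS-SCR) to models of dental environment difference on behavioral outcomes, and examining the change in the within group coefficients". The decision rule follows: "A change in coefficient >15% will be considered evidence of mediation". The same section expects that if mediation is present, "we anticipate that the anticipated effect of environment will be eliminated once we add in EDA to the models specified in Hypothesis 2", which points to attenuation, although the rule itself gives no direction. It also states: "While we have several outcomes, we specify only one mediator".

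Under Secondary Objective 3: Hypothesis 3, the plan says "we will add to the model for Hypothesis 2 above and look at the change in the coefficient and effect size of" B1, and also at the EDA coefficient B2. The Hypothesis 3 model contains a single EDA term and does not say whether EDA enters as a within-child change.

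Other material is to be examined: bivariate EDA–behaviour associations, Cohen's d for environment before and after EDA is added, and a general two-sided alpha of 0.05. None of these is made a condition for declaring mediation, and neither is a significant total effect.

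The effect sizes come from Section 12.2. For the mediator, "the effect sizes for EDA difference between environments ranged from Cohen's d = 0.44-0.46". For the behavioural outcomes, "distress behavior measure effects were small (d's ranging from 0.11 to 0.23"), while sensory discomfort and pain were 0.69 and 0.62.

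**The concern.** A percent change in a coefficient is a ratio. When the denominator is small, a trivial numerator clears 15%. The distress outcomes are in that position: the expected total effect is small and the expected EDA shift is two to four times as large (0.45/0.23 = 2.0; 0.45/0.11 = 4.1). A chance EDA coefficient multiplied by that shift can exceed 15% of the total.

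At stake is the answer to secondary objective (b) for the distress outcomes. A reported mechanism (SADE calms the child physiologically, and that improves behaviour) could rest on noise, at an error rate that nobody has set. The rate changes with the total effect, the EDA effect, N, the number of EDA measures and the model form.

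Two ambiguities add to this. SCL and NS-SCR may be entered together or one at a time. If EDA is not separated into within-child and between-child parts, a correlation that exists only between children can also trigger the rule.

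**Working it through.** **Inputs.** From Section 12.2: 165 children with both visits, EDA d = 0.44–0.46 (0.45 used below), distress d = 0.11–0.23, pain d = 0.62, sensory discomfort d = 0.69. From Section 12.4: the 15% threshold. Assumptions: pilot d's are paired differences standardised by the SD of the differences, the data are normal, and the pilot effects are the true effects.

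**The plan's own figure.** A paired test at two-sided 0.05 with 80% power to detect d = 0.22 needs n = ((1.960 + 0.842)/0.22)² ≈ 163, or 165 with the t distribution. Power at 165 is 0.802. The stated N and d reproduce, which supports reading d as a paired standardised difference. Section 12.2 also states 10% loss from 220 recruited, which is 198, so N = 198 is shown as a variant.

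**Set-up.** Let D_Y and D_M be each child's between-environment differences in behaviour and EDA, each with SD 1. Without EDA, B1 is mean(D_Y). With EDA added, it is mean(D_Y) − b·mean(D_M), where b is the slope of D_Y on D_M. The proportional change is therefore b·mean(D_M)/mean(D_Y), and the rule is met by attenuation when this exceeds 0.15. Under the null, D_Y and D_M are independent (true B2 = 0).

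**Approximate check.** The SD of b is about 1/√N, so the chance indirect effect has SD of about 0.45/√165 = 0.035. The thresholds are:

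- d = 0.11: 0.15 × 0.11 = 0.0165, and 0.0165/0.035 = 0.47 SD, giving an upper tail of about 32%.
- d = 0.23: 0.15 × 0.23 = 0.0345, and 0.0345/0.035 = 0.99 SD, giving about 16%.

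Both thresholds lie within one SD of zero.

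**Simulation** (40,000 trials per setting with one EDA measure, 20,000 with two; true B2 = 0):

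| Setting | d = 0.11 | d = 0.23 |
|---|---|---|
| N = 165, one EDA measure, attenuation > 15% | 31% | 17% |
| Same, N = 198 | 30% | 15% |
| N = 165, change in either direction | 63% | 35% |
| N = 165, SCL and NS-SCR together (correlation 0.3–0.7 assumed) | 33–35% | 20–23% |
| N = 165, among trials with a significant total effect | 19% | 15% |
| N = 165, significant total effect and attenuation, of all trials | 6% | 12% |
| N = 165, EDA effect d = 0.22 | 19% | 5% |
| N = 165, no EDA effect | 5% | 0.5% |
| N = 165, significant B2 also required (not in the plan) | about 2.5% | about 2.5% |

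Power for the total effect in these runs is 29% at d = 0.11 and 83% at d = 0.23. At d = 0.62–0.69 with one EDA measure, attenuation occurs in under 1% of trials, and a change in either direction in under 2%. With two measures attenuation reaches at most about 2.5%.

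**If EDA is not separated.** A random-intercept model with undivided EDA was run with 2,000 trials per cell at d = 0.11–0.23. The ICC (0.3–0.7) and between-child EDA–behaviour correlation are assumptions; the documents give neither. The rule is met in 10–26% of trials at correlation 0, 30–72% at 0.2 and 59–93% at 0.4, with no within-child effect in any of them.

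**The case against.** The strongest defence is that the 15% sentence should not be read alone. The plan starts with the EDA–behaviour associations, looks at B2, sets a two-sided 0.05 and compares effect sizes. On a staged reading, with B2 required to be significant, false claims fall to about 2.5%. But the text never states that requirement. It names one criterion and attaches no condition to it, so an analyst following the plan could declare mediation on the ratio alone.

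Several narrower points stand:

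- At d = 0.11 most trials would show no significant total effect, so 31% includes many trials with little demonstrated effect to mediate. The conditional 19% and 15% are the fairer figures if a significant total effect is presupposed, and they are still high.
- The 17–31% range is for one EDA measure and within-child estimation. Two measures raise it. A random-intercept model with no between-child correlation lowers it.
- The effect sizes come from a pilot with 22 children with ASD, and the distress scales have a restricted range, so normal data are a simplification. A smaller EDA effect shrinks the problem.
- The between-child figures rest on assumed correlations and show only what can happen. The plan's reference to within-group coefficients leans toward within-child estimation without fixing it.
- SCL and NS-SCR can fairly be called two measures of one construct. The plan must still say how both enter the model.
- The objective is secondary and the wording is evidence, not proof. However, the moderator models are labelled exploratory and the mediation analysis is not.

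**Conclusion.** The concern holds. As written, the mediation decision has no error control. For the distress outcomes it would be met by chance attenuation in about 17% (d = 0.23) to 31% (d = 0.11) of trials when EDA has no effect on behaviour. This takes N = 165, an EDA shift of d = 0.45, one EDA measure and a within-child model. The rate is above 5% in every model form tried at the pilot effect sizes; it falls to 5% or less only if the EDA shift is much smaller and the total effect is at the upper end, or if the EDA shift is absent. The missing interval or test is certain from the text. The exact rate depends on the assumptions listed.

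The damage is limited to secondary objective (b), mainly the distress measures. Pain and sensory discomfort are barely affected unless between-child correlation enters the model. The primary comparison of EDA between environments is unaffected.

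**What to change.** Replace the 15% rule in Section 12.4 with a within-child indirect effect. This is the environment effect on EDA multiplied by the coefficient of the SADE–RDE difference in EDA in a model for the SADE–RDE difference in behaviour, adjusted for visit order and the temperature difference. Age and gender can be added as child-level terms. Claim mediation only if the bootstrap 95% interval excludes zero in the attenuating direction. Name one EDA measure in advance, or test the joint SCL and NS-SCR indirect effect. Report percent change as description only. Optionally, apply Holm across the behavioural outcomes or label the mediation results exploratory. Settle the wording before the mediation models are run.

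The cost is SAP text and a bootstrap run, with no new data. In simulation at N = 165 the percentile bootstrap gave false claims in 2.7–3.0% of trials with one EDA measure and 2.2–2.8% with the joint test of two, against 17–32% for the 15% rule in the one-measure runs. Testing the two measures separately without adjustment gave 5–6% (correlation 0.5 assumed). Fewer mediation claims would be made: with EDA d = 0.45 and total d = 0.23, power is about 48%, 75% and 90% for within-child EDA–behaviour correlations of 0.15, 0.20 and 0.25 (500 trials each).

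A smaller repair, requiring B2 to be significant as well, would also bring the false rate to about 2.5%, but it gives no interval for the size of the indirect effect.

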# **Primary Objective: Hypothesis 1**

The primary objective is to test the effect of the environment (SADE vs RDE) on physiological anxiety. Hypothesis 1 specifies an effect of environment on the outcome, thus the main effect of interest will be  $B_1$ , the dental environment.

Hyp 1: EDA =  $B_0$  +  $B_1$ \*Environment + Covariates

## Secondary Objective 2: Hypothesis 2

The secondary objective explores further outcomes and mechanisms of the group differences. Hypothesis 2 is analogous to those in the primary aim and have the same coefficients of interest. However, there are multiple, secondary outcomes including behavioral distress, perception of pain, and sensory discomfort). As noted above, we will apply a rational approach to examination of multiple outcomes and will assess effect sizes of the coefficients, in addition to the statistical significance.

Hyp 2: Negative behavior =  $B_0 + B_1$ \*Environment + Covariates

# **Secondary Objective 3: Hypothesis 3**

Hypothesis 3 seeks to test the degree to which physiological anxiety mediates the effect of the SADE intervention's impact on negative behavior. To test this hypothesis, we will add to the model for Hypothesis 2 above and look at the change in the coefficient and effect size of  $B_1$  as well as the effect of EDA ( $B_2$ ) on negative behavior.

Hyp 3: Negative behavior =  $B_0 + B_1$ \*Environment +  $B_2$ \*EDA + Covariates

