# 3.2 Study Outcome Measures

# 3.2.1 Outcome Measures for the Primary Objective

Our primary outcome measure is children's physiological response measured by EDA during the dental cleaning. EDA will be measured using the BIOPAC Systems, Inc. MP150 System. This physiological response is caused by sympathetic nervous system activation, which increases during stressful or painful situations. Sensors will be placed on the child's fingers and EDA recordings will be made immediately prior to and continuously throughout each cleaning. Two measures of tonic EDA will be collected: skin conductance level (SCL) and frequency of non-specific skin conductance responses (NS-SCR). See Table 1.

Table 1. Primary outcome measure of children's physiological responses for the SADE-2 Study.

Outcome measure (Completed by)	Measure & Description	Type of Measure (No. of Items)	When Administered	Specific Objective Tested	CRF Name (#)
Physiological Anxiety (Researcher- coded)	Electrodermal Activity (skin conductance level and frequency of non- specific responses) assesses level of sympathetic nervous system activation.	Psycho- physiological (N/A: scoring is continuous throughout recording)	Recorded at baseline and throughout both dental cleanings.	1	Scored EDA Form (23)

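### The Hypothesis 3 mediation model adds EDA as a single term and does not separate a child's own SADE-RDE change in EDA from stable differences between children

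*Combined protocol and SAP*

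**What the plan says.** Section 12.4, under Secondary Objective 3: Hypothesis 3, prints a model for negative behaviour with an environment term (B1), one EDA term (B2) and covariates. The stated step is "we will add to the model for Hypothesis 2 above and look at the change in the coefficient and effect size of" the environment term. The estimate of B2 is to be examined alongside it.

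The opening part of Section 12.4 describes the same analysis in two steps. The initial step is "first examining the bivariate relationships between EDA and behavioral outcomes". In the second step the environment models are refitted with the physiological measures included, which the plan words as "adding EDA estimates (SCL and NS-SCR) to models of dental environment difference on behavioral outcomes". The decision rule is: "A change in coefficient >15% will be considered evidence of mediation". No confidence interval or test of the indirect effect is given.

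The environment models to which EDA is added are described as "examining the within-subject factor of dental environment (SADE vs RDE) using repeated measures ANCOVA for each outcome". Section 3.2.1 (Table 1) says EDA is "Recorded at baseline and throughout both dental cleanings", so it takes a different value at each visit.

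The plan does not say whether the EDA estimate is a raw level, a change from the three-minute rest period in Section 6.2, or a value centred on the child. It does not say how the repeated measures ANCOVA is to handle a covariate that differs between the two visits.

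**The concern.** Every child is to be cleaned once in each environment, so the environment contrast lies wholly within the child. If EDA transmits the effect of the environment, it must do so through the child's own change in EDA between the two cleanings.

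EDA also differs between children for reasons unrelated to the environment. Some children may run high on EDA and be more distressed at both visits. A single B2 fitted to visit-level data averages that between-child association with the within-child one. Because the fall in B1 equals B2 times the mean EDA difference, and the environment is expected to shift EDA, a purely between-child association can produce a fall in B1 that looks like mediation. In the opposite case, a genuine within-child effect is diluted when stable EDA and stable behaviour are unrelated.

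Mediation is a named secondary objective, and Section 2 gives it as part of the reason for a larger trial. The answer could reflect how the covariate was coded, or a trait correlation, rather than the mechanism.

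**Working it through.** **The plan's own figure.** The documents give no figure for the mediation analysis. The nearest is in Section 12.2: 165 children with both visits detect d = 0.22. As a paired comparison at two-sided 0.05 and 80% power, n = ((1.960 + 0.842)/0.22)² ≈ 163, or 165 with the t distribution; power at 165 is 80.2%. It reproduces at the 0.05 of Section 12.4. At the 0.025 printed in Section 12.2, 197-199 would be needed. The match supports reading the plan's d values as paired effects, which is how they are used below.

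**Inputs from Section 12.2.** N = 165. Pilot d is 0.44-0.46 for EDA (0.45 used), 0.11-0.23 for distress behaviour, 0.62 for pain and 0.69 for sensory discomfort.

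**Assumed inputs, not in the documents.** ICCs of EDA and behaviour are 0.3-0.7. The correlation r between the stable (child-level) parts of EDA and behaviour is 0, 0.3 or 0.5. The true within-child effect of EDA on behaviour is set to 0.

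**Hand calculation, both ICCs 0.5, total variances 1.**

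1. Between-child slope = 0.5r / (0.5 + 0.5/2) = 0.5r/0.75, which is 0.20 at r = 0.3 and 0.333 at r = 0.5. The within-child slope is 0.
2. A random-intercept fit weights each slope by EDA variance over residual variance at that level. The within-child weight is 0.5/0.5 = 1. The between-child weight is 1/(1 - 0.20²) = 1.042 at r = 0.3 and 1/(1 - 0.333²) = 1.125 at r = 0.5.
3. B2 = 1.042 × 0.20/2.042 = 0.102 at r = 0.3, and 1.125 × 0.333/2.125 = 0.176 at r = 0.5. Pooled regression gives B2 = 0.5r = 0.15 and 0.25.
4. The SD of a paired difference is √(2 × 0.5) = 1, so the share of B1 removed is B2 × 0.45/d. At d = 0.23 this is 0.102 × 0.45/0.23 = 20% and 0.176 × 0.45/0.23 = 34%. At d = 0.62 it is 7% and 13%.

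**Simulation, 165 children, 4,000 runs per setting.** At ICCs of 0.5 the random-intercept B2 averaged 0.100-0.103 at r = 0.3 and 0.176-0.178 at r = 0.5, as in step 3. The share of trials in which B1 falls by more than 15%, with no within-child effect, was:

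| Behaviour d | r = 0 | r = 0.3 | r = 0.5 | Within-child EDA only, any r |
|---|---|---|---|---|
| 0.11 | 25.0% | 76.4% | 89.8% | 30.3-30.7% |
| 0.23 | 10.9% | 63.3% | 92.7% | 17.3-18.7% |
| 0.62 | 0.1% | 5.3% | 30.6% | 0.8-1.0% |
| 0.69 | 0.0% | 3.1% | 21.5% | 0.4-0.6% |

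With EDA ICC 0.5-0.7 and behaviour ICC 0.5, the rates over r = 0.3-0.5 are about 64-97% at d = 0.23 (median fall 19-36%) and 78-91% at d = 0.11. At d = 0.62 they are 4-7% (r = 0.3) to about 34% (r = 0.5). With ICCs across 0.3-0.7, d = 0.23 gives 52-76% at r = 0.3 and 88-98% at r = 0.5; d = 0.62 gives 1-11% and 9-57%. Pooled regression is generally worse: 84% against 63% at d = 0.23, r = 0.3, ICCs 0.5.

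**A test of B2 alone does not rescue the single-term model.** Requiring a significant random-intercept B2 as well as the 15% fall still gives 44% (r = 0.3) and 87% (r = 0.5) at d = 0.23, ICCs 0.5. With within-child EDA the same double requirement is met in 3% of runs or fewer.

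**Literal repeated measures ANCOVA with two EDA columns per child.** If each column is centred at its own mean, B1 cannot move: in one simulated data set it was -0.2528 before and after, while a difference model on the same data gave -0.079. With uncentred columns (ICCs 0.6 for EDA and 0.5 for behaviour, EDA mean 5 SD above zero) and a true within-child slope of 0.4, mean B1 went from -0.227 to -0.059, close to the -0.066 of the difference model, but with an SD of 0.44. With no within-child effect and between-child correlation 0.4, it went from -0.231 to -0.238.

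**The case against.** The strongest reply is that the plan is unspecified here rather than shown to be wrong. It never calls the EDA term raw, the covariate might be adjusted for the rest period, and it names repeated measures ANCOVA, whereas the high false-mediation rates come from random-intercept or pooled fits. A paired-difference fit would use only the within-child slope. All of this is fair. But nothing in Section 12.4 asks for such a fit, and the printed equation has one term and one coefficient. A change from rest would still be one value per visit and could still carry differences between children.

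Three stronger readings are tempting, and the documents do not support them.

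- A reader might infer that the trial will report mediation that does not exist. That needs both a long-form fit and a between-child correlation, which the documents do not give. At correlation 0 there is no excess, and for pain and sensory discomfort a false finding is uncommon unless the correlation is strong.
- A reader might infer that a literal repeated measures ANCOVA can never show mediation. That holds only if each EDA column is centred at its own mean. Uncentred columns recover the within-child slope on average, though B1 is then very imprecise.
- A reader might infer that the bivariate step pools visits and acts as a gate. The text states neither.

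It is also true that part of the false mediation at small d comes from the untested 15% rule, and separating the EDA components does not remove that part.

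**Conclusion.** The concern holds in conditional form. The Hypothesis 3 model does not separate within-child from between-child EDA, and its answer depends on a coding choice that the plan leaves open. Under one natural reading, visit-level EDA in a long-form model, the 15% rule would usually declare mediation for the distress outcomes when the child's change in EDA does nothing, given a moderate between-child correlation. Under another reading, B1 may not move at all or may be too imprecise to use.

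The sizes rest on assumed ICCs and an assumed between-child correlation, on pilot d values read as paired, and on a simulation with one EDA measure, normal data, no period effect and no imputation.

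This should be fixed, but it is not critical. It affects one secondary objective; the primary analysis and the Hypothesis 2 estimates are unchanged.

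**What to change.** Rewrite the Hypothesis 3 model in Section 12.4 as follows.

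- Split each EDA measure (SCL and NS-SCR) into the child's mean over the two visits and the visit's deviation from that mean, with separate coefficients. Equivalently, regress the SADE-RDE difference in behaviour on the SADE-RDE difference in EDA, adjusting for the mean-centred child average of EDA.
- Base mediation only on the within-child coefficient.
- Examine the preliminary EDA-behaviour association on SADE-RDE differences.
- Replace the 15% rule with a confidence interval for the within-child indirect effect. Both changes are needed: with within-child EDA alone, the rule is still met by chance in about 17-20% of trials at d = 0.23 and 31-34% at d = 0.11.

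The cost is SAP wording, with the same data and software. The price is a somewhat less precise B2, because the between-child information no longer contributes to it.
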